- i. Pain, function and quality of life will be assessed using VAS and WOMAC scales. All patients will be evaluated before treatment, and at 1, 3, 6, 9 and 12 months.
- ii. Magnetic resonance with T2 Map imaging will be performed at baseline to analyze cartilage damage and at 6 months control. This test allows the early diagnosis of areas of cartilage degeneration. In addition it evaluates the relaxation times of water, collagen and proteoglycans. Sequence to assess the structure of the cartilage²⁵.

5. Randomization.

A randomized non blind clinical trial with active control. For this purpose, the random number generator, found on the RANDOM.ORG ® website (available at <https://www.random.org/integers/>)²⁶ will be used to generate 31 random numbers. Value between 0 and 1. Format: 5 columns.

[figure not shown]

Figure 1: Study Design. W (week), M (month), V (visit), VAS (visual analogue scale), WOMAC (Western Ontario Mc Master University Osteoarthritis Index)

6. Procedures

a. **Stem cell obtaining procedures.**

All the procedures will be performed in the operating rooms of the Omnihospital by [name] and [name], both certified orthopedic surgeons. Both will know about the randomization in order to know the source from which MSCs will be obtained, in an ambulatory procedure under local anesthesia and sedation. Average procedure time to obtain de MSCs will be approximately 75 minutes.

b. **BM-MSc PROCEDURE. GROUP 1**

- i. Bone marrow aspiration will be performed using a standard surgical technique: fluoroscopically guided percutaneous puncture of posterior iliac crest bone.
- ii. A total of 60 ml of blood from bone marrow will be aspirated with a heparinized syringe.
- iii. Attach the heparinized syringe to a 150 um filter. Gentle push the bone marrow through the filter to another syringe.
- iv. Attach 45 degree dispensing tip to filtered bone marrow 60 cc syringe.
- v. Slowly transfer the BMA into the Neogenesis 60 cc kit concentrating device until you have reached the 60 cc mark. Secure the green cap and clear safety cap.
- vi. Centrifugation of Neogenesis 60 cc concentrating device. Match counterbalance for each concentrating devices +/- 1.0g. Spin at 4200 rpm / 2800 rcf for 10 minutes.
- vii. Place the concentrating device on the BPS (Benchtop processing station), secure the device with your right hand and slowly turn the knob with your left hand counterclockwise, until the bone marrow aspirate has reached the bottom of the luer slip fitting.

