- i. AD-MSC will be joined with BM-MSC in a same syringe for application of the percutaneous injection (AD MSC + BM MSC group) into the affected knee.

7. FOLLOW UP.

All patients will be evaluated measuring scores of the WOMAC (Western Ontario and McMaster Universities Osteoarthritis Index)²³ and the VAS (Visual Analogue Scale), before treatment and then at 1, 3, 6, 9 and 12 months.

STUDY FLOW CHART
MSC IN OA

Patient: _____

STUDY FLOW CHART	VISIT 1	VISIT 2	VISIT 3	VISIT 4	VISIT 5	VISIT 6	VISIT 7	VISIT 8	VISIT 9	VISIT 10
Protocol Concept Sheet	Week 1	Week 2	Week 3	Week 4	Week 6	Month 3	Month 6	Month 9	Month 12	Month 15
Diagnosis	X	X								
Orthopaedic exam	X									
X RAYS		X								
MRI T2 map		X								
Laboratory		X								
Inclusion/Exclusion		X								
Informed Consent		X								
Pre Op Evaluations		X								
VAS		X								
WOMAC		X								
Preparation	X		X							
Randomization				X						
Procedures					X					
BM MSC					X					
AD MSC					X					
Flow Citometry Order					X					
Post Op Evaluations					X					
Sticks removed					X					
VAS						X	X	X	X	
WOMAC						X	X	X	X	
MRI T2 map							X			
Adverse Event Evaluation					X	X	X	X	X	
Results										X

MD. Signature

Date.

[figure not shown]
Figure 2. Clinical Trial MSC/OA Protocol Sheet.

Statistical Analysis.

The sample size is determined using the tool of G*Power VERSION 3.0.10. The parameters are applied for the selected F test, two-way mixed ANOVA (repeated measures, with immediate interaction). Given that none of these approaches have been previously compared, either separately or combined, the calculation was conducted considering a medium effect size ($f=0.25$). We established an error probability α of 0.05 and power of 0.95. We calculated the application of 3 repeated measures, even though 6 measures will be conducted for some variables (i.e., the VAS or WOMAC questionnaire).

Based on this criteria, the sample size would be 54, meaning that each group will consist of 18 individuals. The information previously mentioned is represented in detail in the following table and illustrated in a graph below it.

F tests - ANOVA: Repeated measures, within-between interaction		
Analysis:	A priori: Compute required sample size	
Input:	Effect size f	= 0.25
	α err prob	= 0.05
	Power (1- β err prob)	= 0.95
	Number of groups	= 3
	Repetitions	= 3
	Corr among rep measures	= 0.5
	Nonsphericity correction ϵ	= 1
Output:	Noncentrality parameter λ	= 20.250000

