This study applies descriptive statistics for determining the frequency and proportions for demographic variables (age, gender, education, and ethnicity) and clinical states (severity of knee osteoarthritis, time with disease, comorbidities). Likewise, for calculating the mean and standard deviation of age, WOMAC scores (and each element of the scale) and VAS.

We utilize the two-way mixed ANOVA to compare the differences of means between treatment groups for each dependent variable (WOMAC scores, VAS, and radiological changes). With respect to the WOMAC scores, not only we will analyze the scores in general, but also each score value of the three different components separately (pain, stiffness, function). The tests will determine if there is an interaction between the dependent variable and the factors (independent variables). The factors will be the type of treatment (between subjects) and time (within subjects). For the type of treatment, it

is categorized into: BMSCS only, AD-MSc only, and BM-MSc and AD-MSc combined.

As for the time factor, this will differ according to the dependent variable held for analysis. For example, the analysis of WOMAC and EAV scores will be evaluated in 6 different periods of time. The patients will be asked to respond to our questionnaires three weeks before the intervention and 1, 3, 6, 9, and 12 months after intervention (surgery). With respect to radiological changes, the T2 mapping MRI will be performed twice before the procedure and again six months later.

To guarantee the reliability of the analysis, we will test the atypical values by utilizing box diagrams and the normality with the method of Shapiro-Wilk. Furthermore, the homogeneity of variations will be evaluated with inferential statistic Levene tests, while the homogeneity of covariances with multivariate statistical Box's M test. Consequently, to comply with the hypothesis sphericity, a Mauchly's test will be conducted. In the case of a violation of an assumption, different tests will be utilized.

Finally, in the case of a treatment complication, there will be mixed lineal models generalized for determining the probability of each intervention. The complications considered in this investigation are pain and hematomas in the surgical place where stem cells were extracted, knee pain, and synovial effusion.

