Data will be analyzed using SPSS software version 24.0. for every test, a *p-value* lower than 0.05 will be considered as the statistical significance level.

SAFETY

Absence of immunological reaction and disease transmission due to the fact that MSCs belong to the same patient. Wakitani²⁷ from the University of Osaka Japan demonstrated in an 11-year follow-up study that MSC did not induce tumor growth or infection in any patient treated for cartilage lesions.

Chris and colleagues²⁸ reported no adverse events after using intra-articular injection of 1.0×10^8 AD MSCs in patients with knee OA, and showing improvement of joint function.

Peeters et al²⁹. evaluated 8 studies that involved 844 MSC-treated patients with intra-articular injected culture expansion. They concluded that there are no opposing arguments for the intra-articular application of MSC.

Systematic reviews have all been in favor of the safety in intra-articular - injections of MSCs. However, great caution is warranted with culturing and expansion of MSCs³⁰.

DISCUSSION

The function of MSCs has been explored under the influence of bioactive carriers such as platelet-rich plasma (PRP). Platelets contain greater than 1500 protein based factors

with bioactive ability³¹. This broad spectrum of compounds includes growth factors, peptide hormones, chemokines, fibrin and also proteins with anti-bacterial and fungicidal properties.

Growth factors released by platelets may potentially play a positive role in the up regulation of MSCs. TGFβ1 is seen to reduce collagen type I gene expression and up regulate expression of collagen type II and aggrecan genes³². Further, TGFβ1 works in association with basic Fibroblast Growth Factor (FGF2) to assist in the migration of stromal cells to a site of injury^{30,33}.

The combination of PRP with MSCs in intra-articular injections has shown increased collagen type II expression and reduced chondrocyte apoptosis³⁴.

Most recently, Phase I and II trials using expanded adipose derived MSCs in the treatment of OA have shown MRI evidence of cartilage regrowth³¹. Following a single intra-articular injection of 100 million MSCs, radiological (MRI) follow-up at 6 months showed increased cartilage volume³⁰.

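### The plan leaves its mixed ANOVA for unnamed tests on any assumption violation, and for six-visit outcomes the switch would often fire falsely

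*Combined protocol and SAP*

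**What the plan says.** The Statistical Analysis section sends each dependent variable (WOMAC total, its three components, VAS and the radiological outcome) through a two-way mixed ANOVA with treatment and time as factors. It then lists the checks. For outliers and normality, "we will test the atypical values by utilizing box diagrams and the normality with the method of Shapiro-Wilk". Equality of variances is checked by Levene tests, "homogeneity of covariances with multivariate statistical Box's M test" is added, and Mauchly's test covers sphericity. The consequence of a failed check is one sentence: "In the case of a violation of an assumption, different tests will be utilized".

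The only threshold given is general: "for every test, a *p-value* lower than 0.05 will be considered as the statistical significance level". The section does not say whether normality is tested in each arm-by-visit cell or on residuals, how many rejections make a violation, which violation leads to which test, or which result is then primary. No other section fills these gaps. Study design describes the trial as open label.

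**The concern.** A rule that changes the analysis after looking at the data is acceptable only if both the trigger and the destination are fixed in advance. Here neither is. The mixed ANOVA is the only efficacy analysis the plan specifies, and its interaction test is the basis of the sample size. If chance alone often diverts the analysis, the stated power does not describe the test that is reported. Different outcomes in the same trial could also end up with different tests. Because arm and outcome are both visible, the person who chooses the replacement can see which choice favours which conclusion. The false-positive rate then rests on that choice and cannot be stated beforehand.

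**Working it through.** **1. The plan's own figure.** Inputs from the G*Power table: f = 0.25, α = 0.05, power 0.95, 3 groups, 3 repetitions, correlation 0.5, ε = 1.
- λ = f² × N × m / (1 − ρ) = 0.0625 × 54 × 3 / 0.5 = 20.25, with df 4 and 102. Power is 0.958.
- N = 51 gives λ = 19.125 and power 0.946, so 54 is reproduced.

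That power belongs to the uncorrected interaction F test under sphericity.

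**2. How many checks.** The design gives 3 arms ("the sample size would be 54, meaning that each group will consist of 18 individuals"). For the questionnaires, "the analysis of WOMAC and EAV scores will be evaluated in 6 different periods of time". For MRI, "Magnetic resonance with T2 Map imaging will be performed at baseline to analyze cartilage damage and at 6 months control". The assumption throughout is that one rejection at 0.05 is a violation.

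| Outcome and reading | Shapiro-Wilk | Levene | Box's M | Mauchly | Total |
|---|---|---|---|---|---|
| Six visits, each arm-by-visit cell | 3 × 6 = 18 | 6 | 1 | 1 | 26 |
| Six visits, residuals pooled per visit | 6 | 6 | 1 | 1 | 14 |
| MRI, two time points, each cell | 3 × 2 = 6 | 2 | 1 | none | 9 |

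**3. How often the switch fires when every assumption holds.** If the checks were independent, the rate is 1 − 0.95^k:
- k = 26: 73.6%
- k = 14: 51.2%
- k = 9: 37.0%

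The checks are correlated, so the design was also simulated: 18 per arm, normal data, equal covariances, and the plan's correlation of 0.5.
- 26 checks: 73% (72.8% in 2,500 trials, 73.8% in 8,000).
- 14 checks: 51%.
- MRI: 35%.

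Sensitivity of the 26-check figure:
- Correlation 0, 0.3, 0.7 and 0.9: 72%, 73%, 71% and 59%.
- Median-centred Levene: 69%.
- Box's M judged at 0.001: 72%.
- Five questionnaire time points, as in the study flow chart (15 + 5 + 1 + 1 = 22 checks): 67%.

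The lowest six-visit figure found was 32%. It combines pooled residuals, median-centred Levene, Box's M at 0.001 and correlation 0.9. If any boxplot outlier also counts as a violation, the rate exceeds 99%.

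**4. Correlation that decays between visits.** The plan does not describe the correlation pattern over 12 months, so serial (AR(1)) correlation of 0.5 to 0.8 is an assumption. Mauchly's test then rejects in 98% to 100% of trials. These are correct rejections, because sphericity does fail. The point is only that the unnamed route would then be taken almost always.

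**5. Type I error after the switch.** The fallback is unnamed, so every choice here is an assumption. In trials that pass all checks the uncorrected ANOVA is used.

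| Fallback | Correlation | Overall error rate |
|---|---|---|
| Kruskal-Wallis at 12 months | 0.5 | 5.0–5.1% |
| Rank-transformed mixed ANOVA, Greenhouse-Geisser | 0.5 | 4.8% |
| Greenhouse-Geisser ANOVA | 0.5 | 5.0% |
| Greenhouse-Geisser ANOVA | AR(1) 0.8 | 4.6–6.2% between runs |
| Most favourable of these three, picked after seeing results | 0.5 or AR(1) 0.5–0.8 | about 9–10%; repeat runs gave about 8% |

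The last row is best read as roughly 8–10%.

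**The case against.** Checking assumptions is ordinary practice, and a sponsor would probably respond sensibly, for example by correcting the degrees of freedom when Mauchly's test rejects. That stays within the same ANOVA, so it does not follow that the planned analysis would rarely be used. This part of the objection stands. However, the plan does not say that it would do this, and the correction does not answer a failed Shapiro-Wilk, Levene or Box's M test. In the simulation Shapiro-Wilk alone rejected somewhere in 59% of null trials with per-cell testing.

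The count of 26 is also an inference. The plan does not say that normality is tested cell by cell or that a single rejection is enough. That is why a range is given.

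Two stronger readings are tempting, and the documents support neither.
- A reader might infer that the switch triples the false-positive rate. If the fallback were five uncorrected Kruskal-Wallis tests, one per follow-up visit, the overall rate would be about 15%. Running those five tests always, with no switch, gives 18.0%. The inflation is therefore five-visit multiplicity and not the effect of switching. With a Bonferroni adjustment the switched procedure gives 4.0%. The plan names no such fallback.
- A reader might count against the rule the roughly 9% error of the uncorrected ANOVA under serial correlation 0.8. Under this plan a Mauchly rejection already moves the analysis off that F test, so it would not be reported.

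Nor does the plan say that outliers will be removed; it says only that boxplots will be used to look for them.

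**Conclusion.** The concern holds in a limited form. The plan contains a switching rule with no defined trigger and no named destination, in a trial where the person choosing can see the results. For each six-visit outcome the rule would fire falsely in about half to three-quarters of null trials, and for MRI in about a third. These rates are per outcome, and they are rates of false switching, not of false treatment claims. They assume that one rejection at 0.05 is a violation. No reading tried for a six-visit outcome brings the rate near 5%.

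The type I error cannot be fixed from the documents. A single fallback chosen without regard to results keeps it at about 5–6%. Picking the best of three plausible fallbacks raises it to roughly 8–10%, which rests on the three assumed tests. The text should be changed before any outcome data are examined. This does not make the design unsound.

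**What to change.** Delete the switching sentence and replace it with text to this effect:
- The two-way mixed ANOVA is the analysis for every outcome, whatever the checks show. For the six-visit outcomes the Greenhouse-Geisser correction is always applied. With two MRI time points sphericity does not arise, so no correction is needed.
- Boxplots, Shapiro-Wilk, Levene, Box's M and Mauchly results are reported descriptively and do not change the analysis.
- One sensitivity analysis is named: a rank test on change from baseline to 12 months.

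A linear mixed model adjusted for baseline is an acceptable alternative if it is named in advance. It is partly a matter of preference: with six visits an unstructured covariance has 6 × 7 / 2 = 21 parameters for 54 patients, and the sample-size statement would have to be matched to it.

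The cost is one paragraph of wording, with no extra patients, visits or data. The downside is a small loss of power from the correction when sphericity does hold.

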A total of 54 patients with the diagnosis of knee OA grade II and III will be recruited to receive a single intra-articular injection of MSC: Group 1 (n 18 patients) will receive BM-MSC and Group 2 (n 18 patients) will receive AD-MSC, and Group 3 (n 18 patients) will receive BM-MSC + AD-MSC.

a. Inclusion criteria:

- i. Patients aged 18 to 70 years, with grade II and III knee OA, according to the Ahlbäck classification will be included. Identified by two different observers.
- ii. Minimal VAS pain score of 4.
- iii. Chronic knee pain of mechanical origin.
- iv. All patients who sign a specially prepared informed consent for this clinical trial.

b. Exclusion criteria:

- i. Varus or valgus knee mal alignment superior to 10°.
- ii. OA grade IV according Ahlbäck classification.
- iii. Bone marrow cancer like lymphoma.
- iv. Severe anemia.
- v. Active infections.
- vi. Pregnant patients.
- vii. Immune diseases such as Rheumatoid arthritis, gout or pseudogout arthritis, psoriasis.
- viii. Bone diseases such as Kahler and Paget.
- ix. Corticoesteroid and hyaluronic injections within the last 3 months.
- x. Knee surgery in the last 6 months.

3. Ethical considerations

- a. All patients will be informed of the study aims and have the choice to complete an informed consent.
- b. All patients will be informed about alternative treatments.
- c. This study will be approved by the Ethical Committee of Catholic University of Santiago de Guayaquil (UCSG).

4. Evaluations

a. Pre-Operative:

- i. Complete clinical and orthopedic evaluation.
- ii. Laboratory diagnostic tests (biometrics, coagulation parameters glycemia, and liver, pancreatic, renal and lipid profile).
- iii. Radiological exams: Knee X Rays with weight bearing.
- iv. Magnetic resonance of the knee with cartilage measurement. T2 Map. MRI T2 mapping of the cartilage is a non-invasive functional imaging technique delivering cartography of the T2 relaxation time of the cartilage without any contrast injection. It is sensitive to tissue anisotropy, and provides compositional information on the cartilage collagen network, water content and proteoglycans concentration.

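### The complications analysis rests on a generalised mixed model with 18 patients per arm and no sparse-data method, and it lists knee pain as a complication without limiting it to new or worse pain

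*Combined protocol and SAP*

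**What the plan says.** Main goals, item (b), makes safety an aim alongside efficacy. The analysis of safety is one short paragraph in the Statistical Analysis section. If a treatment complication occurs, "there will be mixed lineal models generalized for determining the probability of each intervention". The complications named are pain and haematoma at the harvest site, "knee pain, and synovial effusion". No link function, random effect, unit of analysis, expected rate or method for sparse counts is given. The descriptive statistics in the same section cover demographics, clinical state, WOMAC and VAS, but not complications. The promise to use other tests when an assumption is violated follows the ANOVA checks and names no test.

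On size, the section states that "the sample size would be 54, meaning that each group will consist of 18 individuals". On entry, Study population, Inclusion criteria, requires "Minimal VAS pain score of 4" (item ii) and chronic knee pain of mechanical origin (item iii). The study flow chart marks adverse event evaluation at Week 6 and at Months 3, 6, 9 and 12.

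**The concern.** There are two separate problems.

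- **Sparse data.** When no patient in an arm has the event, the estimated log-odds for that arm runs off to minus infinity. The odds ratios against that arm, and their Wald tests and intervals, then carry no information. Complications are not summarised anywhere else in the plan, so nothing specified would take their place.
- **Knee pain.** Every eligible patient has knee pain at entry. Listed as a complication with no reference to baseline, grade or timing, it can record the osteoarthritis itself as harm. It also overlaps the VAS and WOMAC pain outcomes, so an arm with better pain relief could look safer for that reason alone.

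The safety half of goal (b) is at stake. The pain hypothesis is not affected.

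**Working it through.** **1. Where 18 per arm comes from.** Inputs from the Statistical Analysis section: f = 0.25, α = 0.05, power 0.95, 3 groups, 3 repeated measures, correlation 0.5, nonsphericity correction 1.

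λ = f² × N × m / (1 − ρ) = 0.0625 × 54 × 3 / 0.5 = 20.25, which matches the printed value. With 4 and 102 degrees of freedom the critical F is 2.461 and power is 0.958. At N = 51 power is 0.946, so 54 is the smallest multiple of 3 that reaches 0.95. The plan's figure reproduces. It sizes the repeated-measures ANOVA only; nothing in it concerns complications.

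**2. Chance of an arm with no events.** Let p be the proportion of patients who ever have a given complication, assumed equal in all arms, with 18 patients in each and no dropout. The documents give no p, so a range is shown.

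P(one arm has 0/18) = q = (1 − p)^18

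P(at least one of three arms has 0/18) = 1 − (1 − q)³

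| Assumed p | q | At least one empty arm |
|---|---|---|
| 2% | 0.695 | 97% |
| 5% | 0.397 | 78% |
| 10% | 0.150 | 39% |
| 20% | 0.018 | 5% |
| 30% | 0.002 | 0.5% |

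Example at 5%: 0.95^18 = 0.397, and 1 − 0.603³ = 0.781. The chance passes one half at p of about 8.4%.

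**3. Sensitivity.**
- Given at least one event in the trial, which is when the plan says the model is used: 96%, 77%, 38% and 5% at rates of 2%, 5%, 10% and 20%.
- Unequal rates of 5%, 10% and 20% in the three arms: 50%. Rates of 20%, 20% and 35%: 4%.
- Five visits per patient, simulated with a patient random intercept (SD 1): an ever-event rate of about 8% gave an empty arm in 52% of trials, and about 19% gave 7%. Repeat visits do not fill an arm in which nobody has the event.

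**4. Harvest-site events.** Section 6 (Procedures) takes bone marrow from the iliac crest in Group 1 and fat from the trochanteric and gluteal region in Group 2; Group 3 receives both products. If harvest complications are analysed by site, one single-source arm is empty by design. If sites are pooled, a Group 3 patient would be expected to have two sites at risk. The plan does not say which applies.

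**5. Knee pain.** Set side by side, the inclusion criteria make knee pain universal at baseline, and the complications list counts knee pain without qualification. If 90% or 95% of patients were counted, the mirror of step 2 applies: the chance that some arm is 18/18 is 39% or 78%. At 100% the outcome does not vary and no treatment effect can be estimated.

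**6. What 18 patients can show.** For 0/18 the exact two-sided 95% upper limit is 1 − 0.025^(1/18) = 18.5%. Against 0/18, another arm needs 5/18 for a Fisher p below 0.05 (p = 0.045).

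**The case against.** - **Event rates are unknown.** A reader might infer that the model will usually fail. The documents do not support that: they state no rates, and nothing says that harvest-site pain or effusion is rare. The one study cited under Safety with no adverse events is weak evidence. From about 20% upward an empty arm is uncommon. This objection stands, so the sparse-data point is conditional.
- **The model may not be fitted singly.** The text does not say that each complication has its own model. If the four were pooled as any complication (assumed independent, equal rates), the any-event rate at 5% each is 1 − 0.95⁴ = 18.5%, and an empty arm has about a 7% chance. At 2% each it is still about 55%. This too stands as a condition.
- **Not everything breaks.** A reader might infer that no usable estimate would remain. In fact the contrast between the other two arms is estimable and a likelihood-ratio test stays finite. Only Wald estimates involving the empty arm are lost.
- **A random effect may have a purpose.** Five adverse event visits give repeated records, so the claim that a random effect could never be estimated is not supported. But the plan does not say that visits are the unit.
- **Knee pain may mean pain attributed to treatment.** The paragraph opens with treatment complications, so calling the item meaningless goes too far. What remains is a definition gap: no section ties the item to new or worsened pain.
- **The list need not limit collection.** The flow chart has a general adverse event row, so other events may be recorded. No analysis of them is written.
- **Sample size is the main limit.** True. An exact test at 18 per arm is also weak (step 6), but an exact interval still gives a readable result at zero.

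**Conclusion.** The point holds in conditional form. With 18 per arm, single-complication models and equal rates, some arm lacks a finite maximum-likelihood log-odds in about 97%, 78%, 39% or 5% of trials at true rates of 2%, 5%, 10% or 20%. The rates are assumptions; the absence of a sparse-data method is a fact of the plan. The figures assume 18 analysed patients in every arm, and a smaller arm is more likely to be empty.

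The knee-pain point needs no assumed rate. It follows from setting the entry criteria beside the complications list, and it is a missing definition rather than proof that the item would be uninformative.

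The change is worth making because simple exact methods serve better than the stated model at this size and cost little.

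**What to change.** In the Statistical Analysis section:

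1. For each complication, report the number of patients with at least one event out of the number treated in each arm, with an exact 95% confidence interval.
2. Compare arms at patient level with the Fisher-Freeman-Halton exact test or Firth logistic regression, named in advance, in place of the mixed model. List repeat events descriptively.
3. State whether harvest-site events are pooled over sites or analysed by site. If by site, compare only the arms that had that harvest.
4. Count knee pain as a complication only when it is new or worse than that patient's baseline. The investigators should set the margin and time window in advance; no value is proposed here. The text schedules a one-month VAS, but the flow chart has no one-month column and no VAS mark at the procedure visit. These should be reconciled so that the reading the definition needs is collected.

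Cost: mainly wording, plus the visit-schedule check in item 4. Exact tests are slightly conservative, patient-level analysis does not model repeat events, and Firth regression may need an add-on to SPSS.
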